### **2.2. Protocol Violations**

Upon assessment of protocol violations, the Sponsor may determine to remove a patient's data from the PP population in an effort to maintain full compliance with study procedures. This will be performed independent of the knowledge of response to therapy. Classification of protocol violation to major or minor will be performed by the study sponsor. The Sponsor or designee will be responsible for producing the final protocol violation file (formatted as a Microsoft Excel file); this file will include a description of the protocol violation and clearly identify

whether or not this violation warrants exclusion from the PP population. This file will be finalized prior to hard database lock.

All protocol violations will be presented in a data listing.

Relevant Output

CCI [REDACTED]

### 3. GENERAL STATISTICAL METHODS

#### 3.1.

CCI

CCI

#### 3.2. General Methods

All data listings that contain an evaluation date will contain a relative study day (Rel Day). Pre-treatment and on-treatment study days are numbered relative to the day of the first dose of study medication which is designated as Day 1. The preceding day is Day -1, the day before that is Day -2, etc. The last day of study medication is designated with an "L" (e.g., Day 14L). Post-treatment study days are numbered relative to the last dose and are designated as Day 1P, Day 2P, etc.

All output will be incorporated into Microsoft Word files, sorted and labeled according to the International Conference on Harmonization (ICH) recommendations, and formatted to the appropriate page size(s).

Tabulations will be produced for appropriate disposition, demographic, baseline, efficacy, and safety parameters. For categorical variables, summary tabulations of the number and percentage of patients within each category (with a category for missing data) of the parameter will be presented. For continuous variables, the number of patients, mean, median, standard deviation (Std Dev), minimum, and maximum values will be presented. Time-to-event data will be summarized using Kaplan-Meier (KM) methodology using 25th, 50th (median), and 75th percentiles with associated 2-sided 95% confidence interval (CI), as well as number and percentage of censored observations and events.

Data will be presented by study part, cohort, and schedule (Part 2 only) as follows:

- Part 1: Cohort A
- Part 1: Cohort B
- Part 1: Cohort C
- Part 2: Cohort A: Schedule 1
- Part 2: Cohort A: Schedule 2

Formal statistical hypothesis testing will be performed on the primary endpoint with all tests conducted at the one-sided 0.10 level of significance for Part 1 and at the two-sided 0.20 level of significance for Part 2. Summary statistics will be presented, as well as CIs on selected parameters, as described in the sections below.

### **3.3. Computing Environment**

All inferential and descriptive statistical analyses will be performed using SAS statistical software Version 9.4, unless otherwise noted. Medical history and AEs will be coded using the Medical Dictionary for Regulatory Activities (MedDRA) Version 16.0 (or later). Adverse events will be graded using Common Terminology Criteria for Adverse Events (CTCAE) Version 4.03 (or later). Concomitant medications will be coded using the World Health Organization (WHO) Drug Dictionary Version Q12013 (or later).

### **3.4. Baseline Definitions**

The baseline for PFS (Parts 1 and 2), OS (Part 1), and duration of stable disease (Parts 1 and 2) is the date of the start of study therapy. The baseline for duration of response is the date of first documented occurrence of response (CR or PR). For all remaining analyses, baseline will be defined as the most recent measurement prior to the first administration of study drug.

### **3.5. Methods of Pooling Data**

Data will be pooled for analysis across all study sites. Separate analysis by-site is not intended, however, data listings will be presented on a by-patient basis, ordered by site and patient identifier.

For each cohort using the Simon 2-Stage design, the DCR results will be presented using data from the first stage of the study and pooled data from both Simon stages together.

### **3.6. Adjustments for Covariates**

No formal statistical analyses that adjust for possible covariate effects are planned.

### **3.7. Multiple Comparisons/Multiplicity**

Multiplicity is not of concern for this early phase study with a single primary efficacy endpoint. The study is designed to look for preliminary evidence of efficacy through inclusion of all the secondary endpoints, but confirmation of these endpoints in a late phase study will be required.

Separate analysis will be performed across each cohort, with separate conclusions regarding efficacy within each cohort; therefore, no adjustment to alpha-level for cohort analysis is required.

### **3.8. Subpopulations**

Part 1 of the study will enroll three cohorts of ovarian (Cohort A), endometrial (Cohort B), and cervical (Cohort C) cancers which will be evaluated independently. Part 2 of the study will enroll additional ovarian patients to evaluate efficacy and safety of once-weekly versus twice-weekly dosing.

Subtypes of each tumor (e.g., adenocarcinoma versus squamous carcinoma) will be evaluated both together and separately as exploratory analyses.

The subpopulation of ovarian cancer (Cohort A) patients who have a baseline CA-125 assessment will be evaluated per the GCIG response criteria in secondary analyses. Within the secondary analyses, a further subpopulation of patients with an initial CA-125 level of at least twice the upper limit of the reference range will be assessed.

### **3.9. Withdrawals, Dropouts, Loss to Follow-up**

Patients will be free to discontinue treatment or withdraw from the study at any time, for any reason, or they may be withdrawn/ removed if necessary in order to protect their health. Patients who are withdrawn from the study will not be replaced.

### **3.10. Missing, Unused, and Spurious Data**

In general, there will be no substitutions made to accommodate missing data points. All data recorded on the electronic case report form (eCRF) will be included in data listings that will accompany the CSR.

No imputation of missing efficacy data is planned, with the exception of partial time-to-event dates. Patients with an event who have only month and year available for the specific time to event analysis will have the event time imputed to the first day of that month. For time to event analyses, patients who have no efficacy evaluations for disease recurrence will be considered censored at time 0. For OS, patients will be censored on the date they were last known to be alive regardless of disease status. For PFS and Duration of SD or DOR, patients without documented PD will be censored on the date of last radiologic disease assessment.

When tabulating time since initial diagnosis, partial dates will be handled as follows. If the day of the month is missing, the day is set to the last day of the month. If the day and month are both missing, the day and month will be assumed to be December 31st.

For AEs, missing dates will not be imputed; however, if partial dates are available, they will be used to assess if the AE occurred during the treatment period and will be imputed according to

the rules outlined below. Missing severities of AEs will not be imputed and will be considered missing in any tabulations of AE severity. If an AE is missing a response to the question regarding relationship to treatment, the event will be considered to be related.

AE Onset date:

If onset date is completely missing, onset date will not be imputed.

If (year is present and month and day are missing) or (year and day are present and month is missing):

- If year = year of first dose, then set month and day to month and day of first dose.
- If year < year of first dose, then set month and day to December 31st.
- If year > year of first dose, then set month and day to January 1st.

If month and year are present and day is missing:

- If year = year of first dose and
  - If month = month of first dose then set day to day of first dose date.
  - If month < month of first dose then set day to last day of month.
  - If month > month of first dose then set day to 1st day of month.
- If year < year of first dose then set day to last day of month.
- If year > year of first dose then set day to 1st day of month.

AE Stop date:

If the outcome of the AE was ongoing or unknown then the rules outlined below will not be applied.

If stop date is completely missing, stop date will not be imputed.

If (year is present and month and day are missing) or (year and day are present and month is missing):

- If year = year of study withdrawal, then set month and day to month and day of study withdrawal.
- If year < year of study withdrawal, then set month and day to December 31st.
- If year > year of study withdrawal, then set month and day to December 31st.

If month and year are present and day is missing:

- If year = year of study withdrawal and
  - If month = month of study withdrawal then set day to day of study withdrawal date.
  - If month < month of study withdrawal then set day to last day of month.
  - If month > month of study withdrawal then set day to last day of month.
- If year < year of study withdrawal then set day to last day of month.
- If year > year of study withdrawal then set day to last day of month.

For prior or concomitant medications, missing or partial dates will be imputed as follows:

Start date:

- If start date is completely missing, start date will not be imputed.

- If (year is present and month and day are missing) or (year and day are present and month is missing), set month and day to January 1.
- If year and month are present and day is missing, set day to the 1st day of month.

Stop date:

- If end date is completely missing, end date will not be imputed.
- If (year is present and month and day are missing) or (year and day are present and month is missing), set month and day to December 31st.
- If year and month are present and day is missing, set day to the last day of month

For the QoL analysis, missing data will be handled as described in the EORTC QLQ-C30 Scoring Manual. If less than half of the scores are missing for any domain, the remaining items will be used applying the standard equations for calculating the scale scores. If at least half of the scores are missing, the scale will be missing. For single item measures, the score will be missing. This method is further described in Section 4.3.

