2. *Response to therapy per GCIG response criteria (RECIST 1.1 and CA-125)*: response for patients in the ovarian cohort will also be assessed for DCR and ORR, as described above, using the GCIG response criteria. Only patients with sufficient data to be assessed based on this criteria (i.e., has a baseline CA-125 assessment) will be included. Number and frequency of patients in the ovarian cancer cohort who can be assessed using the GCIG response criteria will be presented.
3. *Median Progression-free Survival*: PFS for patients in each cohort will be calculated from the date of start of study therapy to the date of progression based on RECIST 1.1, or date of death should progression not have occurred. Patients who drop out prior to study end or do not have documented PD will be censored at the day of last documented disease assessment. The analysis of PFS for patients in each cohort will be based on the Kaplan-Meier method for estimation of summary statistics, and include the 25th, 50th (median), and 75th percentiles and associated 95% CIs. PFS will also be presented with progression defined per GCIG response criteria (RECIST 1.1 and CA-125) for patients in the ovarian cohort with sufficient data to be assessed based on this criteria (i.e., has a baseline CA-125 assessment).
4. *Overall Survival*: OS for patients in each cohort will be calculated from the date of start of study therapy to the date of death due to any cause. OS rate at 12 and 24 months will also be calculated. Patients who drop out prior to study end will be censored at the day they were last known to be alive. The analysis of OS for patients in each cohort will be based on the Kaplan-Meier method for estimation of

summary statistics, and include the 25th, 50th (median), and 75th percentiles and associated 95% CIs.

5. *Quality of Life (QoL)*: will be evaluated for patients in each cohort, and for all study patients combined by EORTC QLQ-C30 after 6 and 12 weeks of treatment and approximately every 8 weeks thereafter.

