### 1.2.5. Efficacy, CCI [REDACTED] and Safety Parameters

#### 1.2.5.1. Efficacy Parameters

The primary efficacy endpoint is DCR, defined as complete response (CR) or partial response (PR) or stable disease (SD) for at least 12 weeks, assessed according to Response Evaluation Criteria in Solid Tumors (RECIST) v1.1. Supportive data will be provided by Duration of SD, calculated from the date of start of study therapy until the date of PD, or last disease assessment should PD not have occurred.

The secondary efficacy endpoints for all cohorts include:

1. Response to therapy per RECIST v1.1, as determined by ORR, defined as either CR or PR per RECIST v1.1, including duration of response (DOR)
2. PFS, calculated from the date of start of study therapy to the date of PD per RECIST v1.1 or date of death if PD does not occur
3. OS, calculated from the date of start of study therapy to the date of death due to any cause, including OS rates at 12 and 24 months
4. QoL, evaluated by the EORTC QLQ-C30

Additional secondary endpoints for the ovarian cancer cohort only include the following:

1. Response to therapy, as determined by DCR, Duration of SD, ORR, and DOR per Gynecological Cancer Intergroup (GCIG) response criteria (RECIST v1.1 and CA-125) (Rustin et al, 2011)
2. PFS, as described above with progression defined per GCIG response criteria (RECIST v1.1 and CA-125)

Data from Part 1 and Part 2 of the study will be analyzed separately for all primary and secondary efficacy endpoints.

CCI [REDACTED]

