## **2. PATIENT POPULATIONS**

### **2.1. Population Definitions**

The following patient populations will be evaluated and used for presentation and analysis of the data:

- **Modified Intent-to-Treat (mITT) Population:** All patients who receive at least one dose of study medication, have measurable disease per RECIST at baseline, and have at least one post-baseline efficacy follow-up information. If the patient has measurable disease per RECIST at baseline, but discontinued treatment prior to the first assessment due to death, toxicity, or PD, they will still be included even if there is no post-baseline efficacy follow-up information. This population will be used for primary analyses of efficacy.
- **Per-Protocol (PP) Population:** All patients in the mITT population who are compliant with study assessments and who have no protocol violations that would compromise the assessment of efficacy. This population will be used for supportive inferences concerning efficacy. If there are major differences between the results in this population and those obtained in the mITT population, this will be taken into consideration in the decision to continue to later phase studies, or in the design of further studies.
- **GCIG Evaluable Population:** All patients in the ovarian cancer cohort (Cohort A) who receive at least one dose of study medication, have measurable disease per RECIST at baseline or a baseline CA-125 assessment, and have at least one post-baseline efficacy follow-up information (i.e. either a post-baseline scan or CA-125 assessment). If a patient discontinued treatment prior to the first assessment due to death, toxicity, or PD, they will still be included even if there is no post-baseline efficacy follow-up information. This population will be used for additional efficacy analyses specific to patients with ovarian cancer.
- **mITT Extended Population:** All patients who receive at least one dose of study medication and have at least one post-baseline efficacy follow-up information. If the patient discontinued treatment prior to the first assessment due to death, toxicity, or PD, they will still be included even if there is no post-baseline efficacy follow-up information. This population will be used for supportive efficacy analyses of select time-to-event endpoints (PFS and OS).

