3. **PFS:** PFS for patients in each cohort will be calculated from the date of start of study therapy to the date of progression based on RECIST 1.1, or date of death due to any cause should progression not have occurred. Patients who do not have documented PD or drop out prior to study end will be censored at the day they were last known to be progression-free (i.e. day of their last evaluable disease assessment). The analysis of PFS for patients in each cohort will be based on the KM method for estimation of summary statistics, and include the 25th, 50th (median), and 75th percentiles and associated 95% CIs.

In addition to being performed on the mITT and PP populations, there will be three additional PFS analyses:

- a. As described above, but performed on the mITT extended population (i.e. including patients with non-measurable disease per RECIST at baseline).
  - b. PFS will also be presented with progression defined per GCIG response criteria (RECIST 1.1 and CA-125). PFS for patients in each cohort will be calculated from the date of start of study therapy to the date of progression based on RECIST 1.1 or CA-125, whichever occurs first, or date of death due to any cause should either type of PD not have occurred. Patients who do not have documented PD will be censored at the day they were last known to be progression-free (i.e. day of their last evaluable disease assessment, either per RECIST or CA-125). This analysis will be performed on the GCIG efficacy population only.
  - c. An additional sensitivity analysis may be performed that includes clinical progression (not documented per RECIST) as an event for PFS. For this analysis, PFS for patients in each cohort will be calculated from the date of start of study therapy to the date of progression based on RECIST 1.1 or date of clinical progression identified by the Investigator, whichever occurs first, or date of death due to any cause should either type of PD not have occurred. Patients who do not have documented PD or drop out prior to study end will be censored at the day they were last known to be progression-free (i.e. day of their last evaluable disease assessment per RECIST). This analysis will be performed on the mITT population.

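### SAP 3.10 censors PFS for every patient without documented progression, with no exception for deaths, although PFS is defined with death as an event

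*SAP*

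**What the plan says.** **Definition.** SAP 1.2.5.1 runs PFS from the start of therapy "to the date of PD per RECIST v1.1 or date of death if PD does not occur". SAP 4.3.2 item 3 runs it to RECIST progression "or date of death due to any cause should progression not have occurred". Protocol 8.4.3 item 3 agrees: "or date of death should progression not have occurred".

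**Censoring.** SAP 3.10 contains three relevant rules in one paragraph. The one that names PFS reads: "For PFS and Duration of SD or DOR, patients without documented PD will be censored on the date of last radiologic disease assessment". A second, covering all time-to-event endpoints, sets the follow-up of anyone never evaluated for efficacy to zero and treats her as censored there. A third gives OS its own rule, with censoring at the latest date of known survival whatever the disease status.

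The censoring sentence in SAP 4.3.2 item 3 also depends on progression alone: "Patients who do not have documented PD or drop out prior to study end will be censored at the day they were last known". It then equates that day with the final evaluable assessment and makes no mention of death. The corresponding sentence in Protocol 8.4.3 item 3 is framed the same way, and Protocol 8.4.1 repeats the time-0 rule.

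**Who is analysed.** Under SAP 2.1, a patient with measurable disease stays in the mITT population if she has had no follow-up assessment "but discontinued treatment prior to the first assessment due to death, toxicity, or PD, they will still be included". The mITT Extended and GCIG Evaluable populations have an equivalent provision. SAP 4.3.2 item 3 uses all three for PFS.

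**The concern.** A patient who dies without documented progression is, by construction, a patient without documented progression. The definition makes her an event on her date of death. SAP 3.10, which names PFS, censors her at her last scan, or at time 0 if she was never scanned. OS has a censoring sentence of its own in that paragraph, while PFS is grouped with duration of SD and DOR. Those two endpoints are consistently defined without death, so the rule suits them but not PFS.

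Two programmers working from the same SAP could therefore produce different PFS curves. The literal reading favours the drug: early deaths leave the risk set instead of counting as failures. PFS is secondary and descriptive, but it is a main efficacy readout for each Part 1 cohort and for the two Part 2 schedules.

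DOR and duration of SD are not part of this point. Leaving death out of them is a choice of estimand, and both documents make it consistently.

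**Working it through.** The plan states no PFS estimate, event count or power, so there is no figure of its own to reproduce. The check sets the rules side by side and then sizes the difference.

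**Step 1: classify three kinds of patient**

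| Patient | Under the PFS definition | Under SAP 3.10 read literally |
|---|---|---|
| Dies before any post-baseline scan | Event at death | Censored at time 0 |
| Scanned without progression, then dies | Event at death | Censored at last scan |
| Alive, no documented progression | Censored | Censored (same) |

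The first two rows conflict. No readable passage says which rule prevails. The readable part of SAP section 5, on changes to planned analyses, does not mention it.

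**Step 2: closed form for deaths before the first scan**

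Inputs:
- Scans at weeks 6 and 12, then every 8 weeks (Protocol 5.1.1).
- *Assumed:* a fraction f die before week 6 without documented progression.
- *Assumed:* exponential progression with a 12-week median in the others, read only at scans.

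Formulas:
- Death as event: S(w) = (1 − f) × exp(−w × ln 2 / 12)
- Literal 3.10: S(w) = exp(−w × ln 2 / 12)
- Ratio, literal to correct: 1/(1 − f)

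| After week | Literal 3.10 | f = 5% | f = 10% | f = 15% | f = 20% |
|---|---|---|---|---|---|
| 6 | 70.7% | 67.2% | 63.6% | 60.1% | 56.6% |
| 12 | 50.0% | 47.5% | 45.0% | 42.5% | 40.0% |

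The f columns give the value with death as an event. For example, at week 12 and f = 10%: 0.90 × 0.500 = 0.450.

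**Step 3: the same in counts**

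The cohort sizes are from Protocol 3.2; the outcomes are assumed.
- Part 1 cohort of 21, 2 early deaths, 13 progression-free after week 6: 13/21 = 61.9% against 13/19 = 68.4%.
- Part 2 schedule of 16, 2 early deaths, 10 progression-free after week 6: 10/16 = 62.5% against 10/14 = 71.4%.

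**Step 4: effect on the median**

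This used 6,000 simulated cohorts under the Step 2 assumptions, with early deaths uniform before week 6 and progression dated at the next scan. The typical median was week 12 under both rules. The two rules gave different medians in these shares of cohorts, where ranges cover repeat runs:

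| Cohort size | f = 5% | f = 10% |
|---|---|---|
| 21 | about 7–8% | about 20–21% |
| 16 | about 19% | about 32–34% |

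**Step 5: deaths spread over follow-up**

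Here 10%, 20% or 30% of all PFS events are assumed to be deaths without documented progression, in a large simulated sample.

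| Assumed true median | 12-week PFS, death as event | 12-week PFS, literal 3.10 (10/20/30%) | KM median in weeks, death as event (10/20/30%) | KM median in weeks, literal 3.10 |
|---|---|---|---|---|
| 8.7 weeks | 38% | 41/45/49% | 12/12/12 | 12 |
| 13 weeks | 53% | 56/59/63% | 20/18.3/15.9 | 20 |
| 19.5 weeks | 65–66% | 68/71/74% | 20/20/20 | 28 |

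In every case the literal rule left PFS unchanged or raised it. Whether the median moves depends on where the curve crosses 50% relative to the scan dates.

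**The case against.** The best reply is that only one reading is sensible. Because death counts only when progression has not occurred, every PFS death is a patient without documented progression. A literal 3.10 would cancel them all and leave the death clause with nothing to do. The neighbouring OS sentence is just as loose: read literally, it would censor patients who have died, and nobody would apply it so. The time-0 rule also has a natural target in living patients who stop for toxicity before any scan. An experienced programmer would probably let the definition in 4.3.2 govern, and that is probably the intent.

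The size also depends on an assumed f. Eligibility requires ECOG 0–1 and a life expectancy of at least 12 weeks, and suspected progression calls for an unscheduled scan, so the higher values of f have no support in the documents. The planned PFS summaries are Kaplan-Meier quartiles; fixed-time rates are planned only for OS. Finally, the table shells and part of SAP section 5 are redacted and may say more.

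Much of this stands, and it limits the consequence. It does not remove the conflict. The reader must override a rule that names PFS. The endpoint-specific sentences in SAP 4.3.2 and Protocol 8.4.3 repeat the same wording, so turning to them does not settle the matter. No readable text gives the definition precedence.

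**Conclusion.** The point holds. SAP 3.10 states a PFS censoring rule that contradicts the PFS definition in both documents, and the affected patients are deliberately kept in the analysis populations.

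If the definition is followed, the bias is zero. If 3.10 is applied literally, progression-free proportions after the first scan are inflated by 1/(1 − f). That is 3.5 percentage points at week 6 for f = 5% (70.7 − 67.2) and 7.1 points for f = 10% (70.7 − 63.6). Under the Step 2 assumptions the typical median does not move, though individual cohorts of 16 or 21 can differ. These sizes rest on assumed values of f, of the median and of the share of events that are deaths. The contradiction itself rests only on the text.

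It should be corrected before the PFS analysis is programmed. It does not affect the primary DCR conclusion.

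**What to change.** Replace the PFS part of the SAP 3.10 sentence with wording such as:

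> For PFS, death from any cause without prior documented PD is an event at the date of death, including death before any post-baseline assessment. Only patients with neither documented PD nor death are censored, at the last evaluable disease assessment, or at time 0 if there is none.

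Make the same change in SAP 4.3.2 item 3, for the main analysis and for analyses a to c, each keeping its own definition of progression. Align Protocol 8.4.1 and 8.4.3. Protocol 8.1 leaves full analysis detail to the SAP, so the SAP edits are the ones that determine the result.

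Leave the definitions of DOR and duration of SD as they are. Leave the SD-duration derivation in SAP 4.3.1 as well: it feeds the 77-day disease-control criterion, and an unscanned death must not be able to count as disease control.

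The cost is a few sentences and the PFS derivation. Death dates are already collected (Protocol 3.2.3 and 5.3.4), and DCR, OS and sample size are unaffected. PFS estimates would fall only if the literal rule would otherwise have been applied.
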